3. STUDY DESIGN

3.1. Study Overview

This is a Phase 1, randomized, multi-center, double-blind, sponsor open, placebo-controlled, single and multiple dose-escalation study to evaluate the safety, tolerability, pharmacokinetics, and pharmacodynamics of PF-06835375 in subjects with seropositive SLE or RA. Both IV and SC routes of administration will be tested.

This study will include two parts: Part A, consisting of approximately eight single ascending dose (SAD) cohorts, and Part B, consisting of approximately 6 multiple ascending dose (MAD) cohorts. Fewer cohorts may be included in each part at Sponsor's discretion. Cohorts in Part A will be initiated sequentially. Subjects in Part B will receive two doses of investigational product (first dose on Day 1 and second dose on Day 29), and will be enrolled concurrently with Part A following the completion of the initial cohorts in Part A (See [Section 3.3](#)). Subjects who are randomized in Part A will not be eligible to participate in Part B of this study.

[figure not shown]
This study will enroll up to a total of approximately 112 subjects at approximately 10 sites.

The study includes a Screening visit to assess eligibility and subsequent visits for a minimum of 16 weeks. Subjects who meet the end of study criteria (See [Section 3.5](#)) will have one follow-up phone call visit which will represent the end of study visit. Subjects, who do not meet the criteria to leave the study at Week 16, will continue with clinic visits every four weeks until Week 52 and then every 12 weeks until they meet these criteria. Overall, subjects are expected to stay in the study approximately 6-12 months (including screening). Subjects who withdraw from the study may be replaced at the discretion of the sponsor. A replacement subject will receive the same treatment as the withdrawn subject.

Both SLE and RA subjects will be enrolled into this study. Minimum disease activity (ie, [CCI](#) [REDACTED] or DAS28 cutoffs) is not required for entry as inclusion criteria. All subjects in both Part A and B will be followed for a minimum of 16 weeks prior to being able to qualify for study completion based on the cellular recovery (See [Section 3.5](#)).

It is at the sponsor's discretion to dose escalate (See [Section 3.4.1](#)), to repeat the same dose, or to test a lower dose based on emerging data.

[CCI](#)

Throughout the study, B cell counts obtained from a CLIA (Clinical Laboratory Improvement Amendments) certified central lab will be used for clinical decision making (inclusion/exclusion criteria, dose escalation, initiation of Part B and for the end of study criteria).

Table 2. Planned Cohorts

Cohort Name	Administration Route	Proposed Human Dose ^a (mg)	Expected Number of Subjects Per Cohort ^c
Part A (SAD)			
A1	IV	0.03	3a, 1p
A2	IV	0.1	3a, 1p
A3	IV	0.3	3a, 1p
A4	IV	1	3a, 1p
A5	IV	3	6a, 2p
A6	IV	10	6a, 2p
A7	IV	30	6a, 2p
A8	IV	100	6a, 2p
Part B (MAD)			
B1	SC	0.3	6a, 2p
B2	SC ^b	1	6a, 2p
B3	SC ^b	3	6a, 2p
B4	SC ^b	10	6a, 2p
B5	SC ^b	30	6a, 2p
X6 ^d	SC ^b	up to 30	Up to 24 total (16a, 8p)

[figure not shown]
Abbreviations: a = active, p = placebo; IV = Intravenous; SC = subcutaneous

a. Doses may be changed based on available emerging safety, tolerability, PK and PD.

b. Route of administration may be changed based on available emerging safety, tolerability, PK and PD.

c. Sponsor may elect to add more subjects into the planned cohorts for any reason, including but not limited to eg, subject withdrawal, higher than expected PD effect, etc. The study will enroll up to a total of approximately 112 subjects.

d. Optional cohort called "X".

Figure 1. Study Schematic

3.2. Sentinel Dosing

In view of the mechanism of action (B cell and cTfh cell depletion), the interval between sentinel subjects and the remainder of the cohort is proposed to mitigate any unanticipated acute safety risks (ie, infusion/injection site reactions). Sentinel dosing will be employed as follows:

- In Part A, for Cohorts A1-A4 (with 4 subjects planned), subjects will be dosed IV at least 24 hours apart. In order to avoid investigator unblinding, the one subject on placebo in these cohorts may be enrolled in any sequence. The sponsor medical monitor will communicate with investigator(s) from each site after dosing of each subject (and prior to dosing of the next subject) in order to determine whether it is safe to proceed with continued dosing within a cohort.

If the sponsor decides to increase the number of subjects in these A1-A4 cohorts, the sentinel dosing will apply only to the first four subjects as described in the paragraph above. After the sponsor medical monitor determines it is safe to proceed, the remaining subjects can be enrolled and dosed simultaneously.

- In Part A, for cohorts A5-A8 (with more than 4 subjects planned), the first two subjects dosed IV will include one PF-06835375 and one placebo subject. If safety and tolerability profile is acceptable in these two subjects, dosing of additional subjects can occur 24 hours after dosing of the first two subjects. These additional subjects within a cohort may be enrolled and dosed simultaneously. The determination to proceed with dosing of additional subjects will be made by the sponsor following communication between sponsor medical monitor and investigator(s) from sites which enrolled sentinel subjects.
- In Part B, for all SC cohorts, sentinel dosing for the first two subjects (as described for Cohort A5-A8 above) will only be employed if a given SC dose level (or higher) was not previously tested in Part A using the IV route of administration. For example, if Cohort A4 (single 1 mg IV dose) has not been tested, sentinel dosing will be used in Cohort B2 (two SC doses of 1 mg). If safety and tolerability profile is acceptable in two subjects after the first of two doses, dosing of additional subjects can occur 24 hours after dosing of the first two subjects.

If in Part B the SC bioavailability is low and the decision is made to change the route of administration to IV, then sentinel dosing in Part B will not be repeated for dose levels already administered in Part A.

Sentinel dosing in either Part A or Part B will not be used if the sponsor elects to test a dose equal to or lower than the highest dose already studied.

3.3. Initiation of Part B

Part B of the study is expected to be initiated after B cell counts in Part A have been depleted to approximately 10 cells/ μ l. B cell counts obtained from CLIA (Clinical Laboratory Improvement Amendments) certified central lab will be used for this determination.

The decision to progress to Part B will be made at a dose escalation meeting following the review of the available data on safety/tolerability, PK and PD from Part A (See [Section 3.4](#)). The first dose in Part B will be administered via SC route. When progressing to Part B, this dose escalation meeting will also include a review of available safety data at the same IV dose level in Part A. In addition, the next IV dose cohort in Part A will be dosed prior to dosing the first dose level in Part B.

3.4. Dose Escalation and Stopping Rules

3.4.1. Dose Escalation

The decision to progress to the next higher dose in Parts A and B will be made following the review of available safety/tolerability, PK and PD data for the preceding dose levels (in a respective Part) and after the sponsor (Medical Monitor, Clinical Pharmacologist and Study Statistician at a minimum) and investigators (with active subjects or subjects enrolled in the dose level under review) determine that it is safe to proceed to the next dose level.

Once Part B has been initiated, dosing in subsequent cohorts in Part B may occur either via SC or IV routes. Specific criteria for dose escalation in Part B are provided below:

- SC route of administration in Part B: dose escalation in SC cohorts in Part B may occur independent of IV cohorts in Part A.
- IV route of administration in Part B: dose escalation in Part B will only occur after subjects have been dosed with a three-fold higher IV dose in Part A. For example, dosing in B2 (two 1 mg IV doses) may commence after dosing in Cohort A5 (single 3 mg IV dose) occurred.

If the decision has been made to dose escalate, it is at sponsor's discretion whether to proceed with dose escalation. It is also at sponsor's discretion whether to repeat the same dose or to test a lower dose based on emerging data. The dose escalation meeting will review infusion and injection site reactions, and the sponsor will provide guidance to Investigators on management of injection/infusion reactions in the subsequent cohort, including the need for pre-medication with corticosteroids.

Review of ongoing safety data will continue after dose escalation has either been completed or stopped and subjects remain active in the study. These meetings will include a similar group as the dose escalation meetings, and will be scheduled every three months at a minimum.

Dose escalation can proceed after the following criteria are met:

- For cohorts with 4 planned subjects, all 4 subjects have been dosed. For cohorts with 8 planned subjects, at least 6 subjects have been dosed, including at least one placebo subject.
- Sponsor medical monitor and investigators who enrolled subjects in a given cohort have reviewed all available safety data for dosed subjects, including:
 - minimum of 2 weeks of safety and tolerability data after the last study drug dose, AND
 - minimum 1 week of PK data after the last study drug dose.
- In Part A, for cohorts A1-A4 (with 4 subjects planned), 4 subjects have completed two weeks post-dose in the study. In Part A, for Cohorts A5-A8 and B1-B5 (with 8 subjects planned), 6 subjects must complete two weeks post-dose in the study.
- The majority of subjects dosed with PF-06835375 in a given cohort have a detectable B cell count (obtained from the CLIA certified central lab; LLOQ = 1 B cell per μ L of blood) for a minimum of 2 consecutive visits at least 2 weeks apart, starting at Week 12. Subjects, who reach detectable B cell counts and withdraw from the study earlier, will be considered as having met this criterion. Subjects who withdraw from the study prior to reaching a detectable B cell count will not be counted in the cohort size (this will be limited to 1 subject per cohort of 4 or 2 subjects per cohort of 8). Investigators will have access only to de-identified B-cell count data to remain blinded.
- The sponsor and majority of investigators with active subjects and/or subjects enrolled in the dose level under review (includes only subjects who received IP) agree to proceed to the next dose level based on the overall safety profile. For the purpose of defining the majority of investigators, only one investigator from each site will be counted.

3.4.2. Dose Escalation Stopping Rules

Dose escalation stopping rules will be used to determine whether the maximal tolerated dose has been attained. Dose escalation will be stopped if it is determined that the limits of safety and/or tolerability have been reached based on the criteria described in this section. This decision will be made after a discussion takes place between the sponsor study team and the investigator. The sponsor study team may not overrule the investigator's decision to stop dose escalation. If dose escalation is stopped because of any of these criteria, additional cohorts may receive the same or lower doses of the investigational product.

The dose escalation will be terminated based on the following criteria:

- If ≥ 2 subjects within a dose cohort develop *Common Terminology Criteria for Adverse Events* (CTCAE) v4.0 Grade 3 adverse event considered to be serious (ie, SAE) in the same organ system, or if 1 subject develops a CTCAE v4.0 Grade 4 or higher SAE, considered related to study drug, and not clearly related to the underlying disease (ie SLE or RA) process, concomitant medications or supplements.
- Laboratory abnormalities known to be associated with B-cell depleting therapies (neutropenia, thrombocytopenia and anemia) will not be considered for this criterion, instead these laboratory abnormalities will be considered for Individual Stopping Rules ([Section 3.4.3](#)).
- If 50% or more subjects within a dose cohort experience a CTCAE v4.0 Grade 3 or higher infusion reaction as defined by the criteria in [Appendix 7](#).
- If a confirmed or probable case of Progressive Multifocal Leukoencephalopathy is observed, the sponsor will hold dosing for all subjects until the benefit risk assessment of PF-06835375 is re-evaluated by the sponsor (See [Section 7.1.14](#)). If the sponsor concludes the benefit risk assessment is favorable, investigators will be consulted on whether to proceed as described in this section.
- If, at any dose level, the mean exposure for the treatment group reaches or exceeds the exposure stopping limit of C_{av} of 261 $\mu\text{g}/\text{mL}$, OR, based on the observed data, the group mean C_{av} of the next planned dose is projected to exceed the exposure stopping limit (See [Section 1.3](#)). Modified doses may be explored if they are not expected to exceed PK stopping criteria.

If any dose cohort is repeated, this additional cohort will be considered a separate cohort for the purpose of this dose escalation stopping rules.

To determine whether any of the above criteria for stopping dose escalation have been met, the sponsor will convene a dose review team meeting between the sponsor (including at minimum Medical Monitor or Clinical Lead, Clinical Pharmacologist and Statistician) and Investigators who have active subjects or who enrolled in the dose cohort under review, to review adverse event(s) and all relevant safety data. This meeting may take place as part of standard dose escalation meeting or ad-hoc based on emerging safety data. Unblinding to determine relatedness to investigational product may be considered.

If any of the above criteria is considered to have been met as determined by unanimous decision of the dose review team members OR if a unanimous decision cannot be reached:

- No further doses should be administered at this dose and no dose escalation will proceed.

- Enrollment of the study may continue at a lower dose or a lower dose cohort may be added to the study.

Otherwise, upon unanimous decision of the dose review team members that it is safe to proceed, one of the following decisions may be made by the sponsor:

- Enrollment of the cohort may resume as planned.
- The cohort may be expanded at the same dose.
- Enrollment of the study may continue at a lower dose or a lower dose cohort may be added to the study.

Unanimous decision is defined as all Investigators who have active subjects or enrolled in the dose cohort under review (one Investigator per site) and sponsor medical representative (medical monitor or clinical lead) agree.

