9.8. Data Monitoring Committee

This study will not use a data monitoring committee. Ongoing safety reviews in support of dose escalation and during the study will be conducted by blinded and unblinded personnel as described in [Section 3.4](#).

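### Section 3.4.2 gives two answers on whether a dose that has met a clinical stopping criterion may be given to a further cohort

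*Protocol*

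**What the plan says.** Protocol Section 3.4.2 has two parts that bear on a dose at which a stopping criterion is met.

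- The introductory paragraph, before the list of criteria, says: "If dose escalation is stopped because of any of these criteria, additional cohorts may receive the same or lower doses of the investigational product".
- The decision procedure, after the list, describes a dose review team meeting. If any listed criterion is considered met, or if the team cannot agree unanimously, two consequences follow: "No further doses should be administered at this dose and no dose escalation will proceed", and "Enrollment of the study may continue at a lower dose or a lower dose cohort may be added to the study".

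The procedure allows the same dose (resuming or expanding the cohort) only in its alternative branch, after the team has unanimously agreed that it is safe to proceed. Unanimity means one investigator per relevant site plus the sponsor's medical representative.

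Three other texts matter. Section 1.3 bars any dose whose predicted exposure would exceed the exposure limit. Section 3.4.2 treats a repeated dose cohort as a separate cohort for the stopping rules. Section 3.2 drops sentinel dosing for any dose at or below the highest already studied.

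**The concern.** Both sentences refer to the same list of criteria, and they answer the same question differently. One permits a new cohort at the stopped dose and attaches no unanimity condition. The other closes that dose unless every relevant investigator and the sponsor's medical representative agree that it is safe.

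This is a first-in-human trial, and Section 9.8 states: "This study will not use a data monitoring committee". The written cohort rules therefore carry much of the protection, although not all of it. If the introductory sentence were relied on, a sponsor could open a cohort at a dose that had just met a clinical safety rule, without the veto that the procedure gives to investigators.

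**Working it through.** No sample size, power or error rate is involved. The check sets the texts against each other, trigger by trigger. The list has six triggers: the serious-event bullet has two limbs, the infusion-reaction bullet one, the PML bullet one and the exposure bullet two. The laboratory bullet is a carve-out, not a trigger.

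| Trigger | Same dose under the introduction | Same dose under the procedure | Does other text settle it? |
|---|---|---|---|
| Two or more Grade 3 serious events, one organ system | Permitted | Closed | No |
| One related Grade 4 or higher serious event | Permitted | Closed | No |
| Grade 3 or higher infusion reactions in 50% or more of the cohort | Permitted | Closed | No |
| PML, confirmed or probable | Permitted | Closed | Own hold on all dosing, with a return route through this section |
| Mean Cav at or above 261 µg/mL | Permitted | Closed | Yes above the limit: Section 1.3, and the same bullet's condition on modified doses |
| Next dose projected above the limit | Permitted | Closed | No, but the current dose is within the limit, so repeating it is reasonable |

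**The two special cases.** For PML, the route back is "If the sponsor concludes the benefit risk assessment is favorable, investigators will be consulted on whether to proceed as described in this section". The section referred to includes the unanimity rule, so consultation alone does not reopen a dose. In the last row, the concern is that the group mean "of the next planned dose is projected to exceed the exposure stopping limit". Here the procedure is stricter than it needs to be, and the introduction gives the sensible answer.

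**Attempts to reconcile the sentences.**

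1. *The introduction describes the safe-to-proceed branch.* It does not fit: in that branch no criterion was considered met, so escalation was not stopped because of one.
2. *The repeat-cohort sentence settles it.* It says how a repeat is counted, not when one is allowed.
3. *The procedure is more detailed, so it prevails.* This is a reasonable inference, but no text states it.

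**What follows if the introduction is used.**

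- *Further active subjects at the stopped dose.* The procedure gives 0. Under the introduction the number is not fixed, because no text sets the size of an additional cohort. At the planned sizes in Table 2 it would be 3 (as in A1-A4) or 6 (as in A5-A8 and B1-B5).
- *Stopping count.* The repeat is a separate cohort, so the count starts again. After two Grade 3 serious events in one organ system, a third in the repeat cohort (2 + 1 = 3 at that dose) would not trigger the rule. For infusion reactions in a cohort of 8, the threshold is 0.5 × 8 = 4. A repeat cohort of 8 with 3 reactions (3/8 = 37.5%) would not trigger it, although 4 of 8 had already reacted. For the Grade 4 limb the restart changes nothing, since one event triggers it in any cohort.
- *Sentinel dosing.* The dose has been studied already, so Section 3.2 would not require it.

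**The case against.** The best defence is that the texts do not compel opposite actions. The introduction only permits; the procedure directs. Sponsor and sites comply with both by following the procedure, and a specific procedure ordinarily prevails over a general permission. Also, the safe-to-proceed branch offers resuming, expanding or going lower, but no escalation. That resembles the introduction's wording, which may have been meant to summarise the whole process.

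Much of this stands. There is a safe path, and nobody is forced into a breach. What remains is that the introduction ties its permission to a stop caused by a criterion, and nothing ranks the two sentences.

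Other protections also exist: reviews by blinded and unblinded personnel (Section 9.8), written sponsor approval before each subject is dosed (Section 6.1), safety reviews at least every three months once escalation has ended (Section 3.4.1), and a bar on the sponsor overruling an investigator's decision to stop escalation (Section 3.4.2).

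A reader might also cite the general discretion in Section 3.1 "to repeat the same dose, or to test a lower dose based on emerging data" as support for re-dosing at a stopped dose. That carries little weight. The same sentence gives discretion to escalate, and no one would read it as overriding the stopping rules.

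**Conclusion.** Section 3.4.2 is internally inconsistent and should be corrected. The unresolved part is three of the six triggers, all clinical. The difference is 0 further active subjects at the stopped dose against 3 or 6, assuming an additional cohort takes a planned size from Table 2.

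Four stronger conclusions might be inferred, and the documents do not support them:

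- *That observed exposure is equally open.* Section 1.3 and the exposure bullet itself already bar a same-dose cohort above the limit.
- *That PML leaves the dose open on the introduction's terms.* It has its own hold, and its return route leads back into the section's decision procedure.
- *That the size should be taken from optional cohort X6.* X6 is listed as subcutaneous at up to 30 mg (route changeable), is not designated as a repeat of a stopped dose, and is reported as not used in SAP Section 2.1.
- *That the permission was actually used.* SAP Section 2.1 reports reduced doses and unused cohorts, but gives no reason for them. Nothing shows that a criterion was met or that the introductory sentence was relied on.

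**What to change.** Amend two sentences in Protocol Section 3.4.2.

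1. In the introductory paragraph, replace the permission for the same or a lower dose with: *lower doses only, per the dose review procedure in this section, except that the same dose may be used when the only criterion met is that the next planned dose is projected to exceed the exposure limit.*
2. State the same single exception at the bullet that closes the dose.

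Add no exception for PML. Any return to dosing after a PML hold should stay subject to the dose review team's unanimous decision, since an exception based on consultation alone would weaken the present rule.

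The cost is two edited sentences in an amendment, with no added subjects, visits or samples. The change removes only same-dose cohorts that the procedure already forbids, and it relaxes the procedure only for the projected-exposure case. The SAP already lists an actual dose, or non-use, for every cohort, so the practical gain may lie mainly in the trial record and in any later protocol that reuses this text.

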3.4.3. Individual Stopping Rules

If an individual subject develops any of the following, the subject will not receive a second dose of IP in Part B. Subjects in Part B (MAD cohort) who meet these criteria and who have received the first dose of IP will remain in the study and continue to be followed per the [Schedule of Activities](#):

- Laboratory values meeting criteria for potential drug induced liver injury (see [Section 8.4.2](#)).
- Illness or clinical adverse event that prevents daily activity and requires medical intervention (ie CTCAE v4.0 Grade 3).
- Any serious adverse event (irrespective of relatedness to study drug).
- Any infection requiring the use of oral or parenteral antibiotics between first and second dosing of IP requires approval by sponsor clinician or medical monitor prior to subject receiving a second dose of IP.
- Increase in SLE or RA disease activity requiring use of prohibited medications (See [Appendix 2](#)), OR doses or formulations of medications inconsistent with those allowed (See [Appendix 3](#)).
- Prior CTCAE v4.0 Grade 4 infusion reaction during first infusion.

The following criteria will not be considered as Individual Stopping Rules (due to the anticipated effects of PF-06835375 on blood counts):

- Lymphopenia: CTCAE v4.0 Grade 2 lasting 14 days or less OR Grade 3 lymphopenia lasting 7 days or less. For subjects with abnormalities present on Day 1 prior to dose (ie, CTCAE v4.0 Grade 1 or 2), a two-grade shift lasting 14 days or less.
- Neutropenia: CTCAE v4.0 Grade 2 lasting 7 days or less OR Grade 3 lasting 3 days or less.
- Thrombocytopenia: CTCAE v4.0 Grade 2 lasting 7 days or less OR Grade 3 lasting 3 days or less.

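### Cytopenias taken out of the SAE-based escalation stop are referred to a rule that can only withhold the second Part B dose, bounds two of them only by exemption, and omits anemia

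*Protocol*

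**What the plan says.** Protocol 3.4.2 ends escalation on any of several criteria. The SAE-based one is met by two or more subjects in a cohort with Grade 3 SAEs in the same organ system, or "if 1 subject develops a CTCAE v4.0 Grade 4 or higher SAE, considered related to study drug", provided the event is not clearly due to the underlying disease or to other medication. The next bullet takes three findings out: "Laboratory abnormalities known to be associated with B-cell depleting therapies (neutropenia, thrombocytopenia and anemia) will not be considered for this criterion". It then redirects them: "instead these laboratory abnormalities will be considered for Individual Stopping Rules".

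To decide whether a criterion is met, a dose review team of sponsor and investigators meets. If the team finds unanimously that it is met, "OR if a unanimous decision cannot be reached", the consequence is: "No further doses should be administered at this dose and no dose escalation will proceed".

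Protocol 3.4.3, where the three findings are sent, opens: "If an individual subject develops any of the following, the subject will not receive a second dose of IP in Part B". Its triggers include any SAE, related or not. Blood counts appear only in a closing list of what will not count:

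- neutropenia and thrombocytopenia: Grade 2 for up to 7 days, or Grade 3 for up to 3 days
- lymphopenia: Grade 2 for up to 14 days, or Grade 3 for up to 7 days, with a separate allowance for a two-grade shift from an abnormal pre-dose value

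Anemia is not mentioned.

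Ordinary escalation under 3.4.1 requires that the medical monitor and the cohort's investigators "have reviewed all available safety data for dosed subjects". It also requires agreement on the overall safety profile by "The sponsor and majority of investigators with active subjects and/or subjects enrolled in the dose level under review", and detectable B cells in most active subjects at two consecutive visits from Week 12.

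**The concern.** The referral does not perform the function that was removed. Section 3.4.2 governs whether a dose level and the escalation go on; 3.4.3 governs one subject's second injection. An event moved from the first to the second no longer counts toward the formal escalation stop, and in Part A it has no formal consequence at all.

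Protocol 1.6 names neutropenia, thrombocytopenia and anemia as risks seen with other depleting antibodies. That supports tolerating low-grade changes, but it is a weaker basis for an exclusion without a grade cap in a first-in-human study that has no data monitoring committee. The exclusion also fits the stated pharmacology poorly: 1.2.6 reports falls in lymphocytes and white cells as expected, yet lymphopenia is not on the excluded list and still counts.

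At stake is which procedure handles a related, serious, Grade 4 laboratory cytopenia. Any other related Grade 4 SAE goes to a team that must be unanimous to proceed. This one is left to 3.4.1, where sponsor-plus-majority agreement is enough. In Part B there is a second, smaller issue: a site cannot read from 3.4.3 at what count or duration a non-serious cytopenia bars dose 2.

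**Working it through.** **1. Where each event lands** (Protocol 3.4.2 and 3.4.3 side by side; events assumed not clearly due to disease or other medication)

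| Event | SAE-based stop, 3.4.2 | Action, 3.4.3 |
|---|---|---|
| Related Grade 4 SAE outside the exclusion | Met by 1 subject | Dose 2 withheld in Part B |
| Related serious Grade 4 lymphopenia | Met by 1 subject (not excluded) | Dose 2 withheld in Part B |
| Related serious Grade 4 laboratory neutropenia, thrombocytopenia or anemia, Part B before dose 2 | Never met | Dose 2 withheld by the any-SAE trigger |
| Same event, Part A or after dose 2 | Never met | No dose left to withhold |
| Related Grade 4 serious infection or bleeding after a cytopenia | Met by 1 subject (not a laboratory abnormality) | Dose 2 withheld in Part B |
| Non-serious neutropenia or thrombocytopenia beyond the exempted grade or duration | Not an SAE | No written trigger |
| Non-serious laboratory anemia | Not an SAE | No entry |

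The other 3.4.2 criteria (infusion reactions, PML, the exposure limit) do not cover these events. The nearest clinical trigger in 3.4.3 is an illness or clinical event that prevents daily activity and needs intervention. A count without symptoms does not plainly fit it, and it would not explain why Grade 2 counts need exempting.

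**2. Limits implied by the exemptions.** Reversing the closing list gives:

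- neutropenia or thrombocytopenia: Grade 2 for more than 7 days, Grade 3 for more than 3 days, or Grade 4
- lymphopenia: Grade 2 for more than 14 days, Grade 3 for more than 7 days, or Grade 4, subject to the baseline-shift allowance
- anemia: nothing can be inferred

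**3. How many subjects 3.4.3 cannot reach** (Protocol Table 2). Total: 4×(3+1) + 4×(6+2) + 5×(6+2) + (16+8) = 16 + 32 + 40 + 24 = 112, matching the stated enrollment. Active subjects in Part A: 4×3 + 4×6 = 36. Active in B1 to B5: 5×6 = 30. Active in the optional cohort: 16.

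- Without the optional cohort: 36/(36+30) = 36/66 = 54.5%.
- With it: 36/(36+30+16) = 36/82 = 43.9%.
- Cohorts the SAP lists as used (A1 to A6, B1 to B5), at planned sizes: 24/(24+30) = 24/54 = 44.4%.

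**4. How long 3.4.3 can act in Part B.** Day 1 to Day 29 is 28 days, out of the 112 days from Day 1 to Day 113 (Week 16). This is a window, not a risk.

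**5. Whether duration limits can be checked.** Scheduled Part B safety labs after Day 1 and up to dose 2 fall on Days 2, 4, 8, 15 and 29. The gaps are 2, 4, 7 and 14 days. With the visit windows (Days 12–18 and 26–32) the last gap runs from 26−18 = 8 to 32−12 = 20 days. A limit of more than 3 or more than 7 days cannot be confirmed there from scheduled draws. The existing exemptions have the same problem.

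**6. Frequency.** Neither document gives a cytopenia rate. For scale only, under assumed true rates p of related serious Grade 4 or higher cytopenia per active subject, the chance that at least one of n active subjects has one is 1−(1−p)^n.

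| p (assumed) | n = 3 | n = 6 |
|---|---|---|
| 5% | 14.3% | 26.5% |
| 10% | 27.1% | 46.9% |
| 20% | 48.8% | 73.8% |
| 30% | 65.7% | 88.2% |

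Under the current text these events cannot meet the SAE-based criterion at any rate.

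**The case against.** The strongest reply is that the exclusion is deliberate and other text does most of the protecting.

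- **Seriousness.** Section 8.2.3 gives blood dyscrasias without hospitalization as an example of an important medical event, and 8.1 lets the sponsor upgrade a non-serious event. Many Grade 4 counts would therefore become SAEs and bar dose 2. This stands, and it narrows the Part B gap considerably.
- **Eligibility check.** A Part B schedule footnote asks sites to confirm eligibility before admission, and exclusion 3 covers laboratory abnormalities that raise risk. This helps only partly: the admission wording fits the outpatient Day 29 visit poorly.
- **Escalation gates.** Section 3.4.1 requires review of all available safety data, agreement of the sponsor and a majority of investigators, and B-cell recovery. Two visits at least 2 weeks apart from Week 12 mean about 14 weeks or more of data in most active subjects, early withdrawals aside. The sponsor is unblinded, may call an ad-hoc review, and may not overrule an investigator's decision to stop. These safeguards are real, but they are matters of judgement or timing. The no-overrule sentence sits in a paragraph tied to the 3.4.2 criteria, so its reach to excluded events is uncertain.
- **Governance.** Unanimity versus sponsor-plus-majority is a design preference. That is fair for Grade 3. It does not explain a referral that has no effect in Part A.
- **Timing.** The SAP already reports actual doses and unused cohorts, so an amendment may come too late for this trial's escalation. That limits the practical gain here, not the reading of the rule.

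A reader might infer that 3.4.3 has no cytopenia limits at all, or that the protocol permits dose 2 after any Grade 4 neutropenia. Neither is supported: bounds exist for neutropenia and thrombocytopenia in exempting form, and the any-SAE trigger together with 8.2.3 catches much of the rest.

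**Conclusion.** The cross-reference is defective as written. Laboratory neutropenia, thrombocytopenia and anemia of any grade cannot meet the SAE-based escalation stop, and the section they are sent to can act only on the second Part B dose. Two gaps remain.

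- **Escalation, both parts.** A related, serious Grade 4 or higher laboratory cytopenia does not by itself invoke the dose review procedure. In Part A and after dose 2 it has no consequence under 3.4.3 either.
- **Dose 2 in Part B.** Mainly non-serious cytopenia beyond the exempted grade and duration, plus laboratory anemia, has no stated trigger. The amendment log refers to meeting an individual stopping criterion for lymphopenia, so limits appear to have been intended and this is largely a wording repair.

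It would go too far to infer that escalation is unguarded against cytopenia: clinical consequences still count under 3.4.2 and the 3.4.1 gates still apply. The size is structural, namely the share of active subjects beyond the reach of 3.4.3 (about 44% to 55%, depending on the cohorts counted, at planned sizes). No event frequency can be claimed. The reading assumes that the exclusion covers laboratory findings only, as its wording indicates.

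**What to change.** 1. **Section 3.4.3.** State the limits in step 2 of the working as positive triggers for withholding dose 2, keeping the lymphopenia baseline-shift exemption, and add an anemia limit set by the sponsor.
2. **Section 3.4.2.** Cap the exclusion at Grade 3. A related, serious Grade 4 or higher laboratory neutropenia, thrombocytopenia or anemia then goes to the existing dose review procedure in both parts.

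The cost is amendment wording plus some operational burden. Item 1 means an occasional withheld second dose and extra blood counts between Day 15 and Day 29; Protocol 7.1.1 already allows unscheduled draws. Item 2 means additional review meetings, and its main price should be stated openly: the team may still proceed if unanimous, but a single dissent would halt that dose level and the escalation. How often that would arise depends on a rate the documents do not give. If the sponsor finds that price too high, item 1 can be adopted alone, but that leaves the escalation gap open.
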